# 6.4.2 Reporting Requirements for this Study

The Serious Adverse Event (SAE) Reporting Category, as defined in Version 2.0 of the DAIDS EAE manual, will be used for this study (the definition of an SAE is also included in the manual).

In addition to SAEs, sites will report in an expedited manner the following results (must be both in order to require expedited reporting): ALT\ge 3xULN AND bilirubin\ge 2xULN.

These reporting requirements are required for each study participant from enrollment (week 0) until their follow-up in the study ends. After this time, sites must report serious, unexpected, clinical suspected adverse drug reactions if the study site becomes aware of the event on a passive basis, i.e., from publicly available information.

The study agents for the purposes of EAE reporting are GSK1265744 30 mg oral tablet or placebo and 744LA injectable suspension (200mg/mL) or placebo (also outlined in Section 4.1.).

### **Grading Severity of Events**

The Division of AIDS Table for Grading the Severity of Adult and Pediatric Adverse Events, December 2004, clarification August 2009 (or latest version) must be used for determining and reporting the severity of adverse events. The DAIDS grading table is available on the DAIDS RSC website at http://rsc.tech-res.com/safetyandpharmacovigilance.

In addition to submitting EAE information to the DAIDS Safety Office via DAERS, the site investigator may be required to submit AE and EAE information to local regulatory agencies or other local authorities.

Information on Grade 1 and higher AEs will be included in reports to the US FDA, and other government and regulatory authorities as applicable. Site staff will report information regarding AEs to their IRB in accordance with all applicable regulations and local IRB requirements.

# **6.5** Social Impact Reporting

It is possible that participants' involvement in the study could become known to others, and that a social impact may result (i.e., because participants could be perceived as being HIV-infected or at risk or "high risk" for HIV infection). For example, participants could be treated unfairly, or could have problems being accepted by their families and/or communities. A social impact that is reported by the participant and judged by the IoR/designee to be serious or unexpected will be reported to the responsible site's IRBs at least annually, or according to their individual requirements. Social impacts will be collected and reported on CRFs during regular visits. In the event that a participant reports a social impact, every effort will be made by study staff to provide appropriate care and counseling to the participant as necessary, and/or referral to appropriate resources for the safety of the participant. Each site will provide such care and counseling in accordance with standardized guidance in the SSP Manual. While maintaining participant confidentiality, study sites may engage their CAB in exploring the social context surrounding instances of social impacts, to minimize the potential occurrence of such an impact.

# 7.0 STATISTICAL CONSIDERATIONS

# 7.1 Review of Study Design

This is a Phase IIa, randomized, multi-site, two-arm, double-blinded study of the safety, tolerability, pharmacokinetics and acceptability of 744LA. Eligible participants will be randomized 3:1, stratified by gender, to receive GSK1265744 or matching placebo. Participants will receive daily 30 mg oral 744 tablets or matching placebo for 4 weeks, followed by a one week washout period, to assess for safety and tolerability prior to receiving injections. Following clinical review of safety lab assessments from the oral regimen phase, participants will enter the injection phase and receive IM injections of 744LA or placebo at three time points at 12 week intervals. IM injections will consist of 800 mg of 744LA or a matching vehicle control, and administered as two 400 mg injections. Participants in the active drug arm will be followed for 52 weeks following their last injection. Participants in the placebo arm will be followed until 52 weeks after their last injection or until the last participant in the active study product arm completes their Week 41 visit, whichever comes first, at which time the study will be unblinded to assess the primary endpoint. When all procedures related to unblinding are completed, participants in the placebo arm will no longer be followed.

176 participants will be randomized 3:1, stratified by gender, as follows:

Arm 1: 132 participants will receive daily oral GSK1265744 (30 mg tablets) for 4 weeks, followed by a one week washout period, to establish safety and tolerability, followed by two IM administered injections of 400 mg (800 mg total) of 744LA at three time points at 12-week intervals as: Week 5, Week 17, and Week 29.

Arm 2: 44 participants will receive daily oral matching placebo and IM injections of vehicle-matched placebo on the same schedule as Arm 1.

# 7.1.1 Primary Endpoint

Safety endpoint: Proportion of participants experiencing any Grade 2 or higher clinical AEs and laboratory abnormalities that occur from the initial injection to Week 41 among participants who receive at least one injection (injectable phase only)

Tolerability endpoint: Proportion of participants who receive at least 1 injection and who discontinue receiving injections prior to the full course of 3 injections due to intolerability of injection (including but not limited to ISR), frequency of injections, burden of study procedures, or any AE.

# 7.1.2 Secondary Endpoints

- Proportion of participants who discontinue either oral or injectable study product for reasons
  of toxicity, tolerability, or acceptability prior to completion of the full oral and injectable
  phases
- Proportion of participants experiencing Grade 2 or higher clinical AEs and laboratory abnormalities during 52 weeks following final injection (safety) and any AE that leads to discontinuation (tolerability) during the aggregate oral and injectable phases
- Proportion of participants experiencing Grade 2 or higher clinical AEs and laboratory abnormalities (safety) and any AE that leads to discontinuation (tolerability) in the oral phase and washout period
- Plasma drug levels of GSK1265744 at designated time points after each injection of 744LA
- Plasma drug levels of GSK1265744 at designated time points after each injection of 744LA stratified by age, gender, race, ethnicity, weight, BMI, and smoking status
- Proportion of participants willing to use an injectable agent such as the study product for HIV prevention in the future
- Change from enrollment of self-reported sexual behavior (number of sexual partners, episodes of unprotected anal and/or vaginal intercourse) during the study period using a standardized assessment tool
- Number of incident HIV infections through the study period, including number with treatment emergent resistance
- Proportion of injectable hormonal-contraception-using female participants who reach a safety or tolerability endpoint as defined above

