### 2.2 Secondary Objectives

- Evaluate the safety and tolerability of GSK1265744 (daily oral 744 + 744LA) for 52 weeks of follow-up after final injection
- Evaluate the safety and tolerability of oral 744 from Week 0 to Week 5
- Evaluate the pharmacokinetics of 744LA administered as 800 mg IM every 12 weeks for 52 weeks of follow-up after final injection

- Evaluate differential pharmacokinetics of 744LA in participants by age, gender, race, ethnicity, weight, body mass index (BMI), and smoking status
- Evaluate the acceptability of 744LA injections
- Evaluate the effect of 744LA on sexual risk behavior by change from enrollment for repeat assessments to during the study period
- Evaluate HIV incidence and antiretroviral drug resistance, if any participants acquire HIV infection during the study
- Evaluate the safety, tolerability and pharmacokinetics of 744LA in the subset of women who use a hormone-based contraceptive

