#### 5.12 Week 81 – Final Visit

Administrative, Behavioral, and Regulatory Procedures

- HIV counseling
- Offer condoms and lubricant

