# 5.15 Procedures for Participants Who Do Not Complete the Full Course of Injections

Participants who received the Week 5 (Injection #1) and Week 17 (Injection #2) injections but will not receive the final injection (Injection #3) will be followed for 52 weeks after their Week 17 injection, through to Week 69. Because participants meeting these criteria received an injection at Week 5 and Week 17, the procedures for Weeks 6, 9, 13, 18, and 23 Safety Visits as outlined above and in the Schedule of Evaluations and Procedures will remain the same. Procedures for subsequent study visits for these participants are outlined in Appendix II.

Participants who received the Week 5 injection (Injection #1) and will not receive the next two injections will be followed for 52 weeks after their Week 5 injection, through to Week 57. Because participants meeting these criteria received an injection at Week 5, the procedures for Weeks 6, 9, and 13 Safety Visits as outlined above and in all Schedule of Evaluations and Procedures will remain the same. Procedures for subsequent visits for these participants are outlined in Appendix III.

Participants who are unable to receive the first injection for any reason will be terminated from the study. If the reason is due to HIV infection or pregnancy, refer to Section 5.17 and 5.19, respectively.

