# **Safety Endpoints**

The primary safety analysis will include Grade 2 or higher clinical and laboratory events that occur from the initial injection to 12 weeks after the last injection among participants who receive at least one injection. Secondary safety analyses will include the same definition applied over the oral phase only (week 0 to week 5) and the aggregate oral+injectable+follow-up period.

To assess safety, the number and the percent of participants experiencing each safety endpoint will be tabulated by study arm. Each participant will contribute once in each category (for example, only for the highest severity AE for each participant) for the calculation of event rates. Exact binomial confidence intervals will be calculated for each safety endpoint for each arm and Fisher's exact test used to test for differences in event rates between the two arms. No formal treatment comparisons will be performed in this study, so any p-values that are calculated should only be used as a descriptive statistic. No formal multiple comparison adjustments will be employed for safety endpoints.

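### Sections 7.1.2 and 7.6.2 give different time windows for the secondary Grade 2 or higher safety proportion, and the objective in 2.2 does not settle which is meant

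*Protocol*

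**What the plan says.** Three places in the protocol bear on this endpoint.

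- **Objective (section 2.2):** "Evaluate the safety and tolerability of GSK1265744 (daily oral 744 + 744LA) for 52 weeks of follow-up after final injection".
- **Endpoint (section 7.1.2):** the matching bullet has two halves. The safety half counts Grade 2 or higher clinical events and "laboratory abnormalities during 52 weeks following final injection (safety"). The tolerability half counts "any AE that leads to discontinuation (tolerability) during the aggregate oral and injectable phases".
- **Analysis (section 7.6.2, Safety Endpoints):** the primary analysis runs from the first injection to 12 weeks after the last. The secondary safety analyses are described as "the same definition applied over the oral phase only (week 0 to week 5) and the aggregate oral+injectable+follow-up period".

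The schedule fixes the weeks. Injections are given "at three time points at 12-week intervals as: Week 5, Week 17, and Week 29", and the last visit is headed "5.12 Week 81 – Final Visit". Under section 5.15, participants with two injections "will be followed for 52 weeks after their Week 17 injection, through to Week 69", and those with one "will be followed for 52 weeks after their Week 5 injection, through to Week 57".

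Section 1.2.4 gives two reasons for following participants for 52 weeks after the last injection. The first is to assess safety events while drug is still detectable in plasma.

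**The concern.** The oral-phase endpoint in 7.1.2 has a matching analysis in 7.6.2. The post-injection endpoint does not. Its window starts at the last injection; the nearest analysis window starts at Week 0 and takes in the oral lead-in, the washout and any earlier injection intervals.

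The two windows classify people differently. Take a participant with three injections whose only Grade 2 event is an injection-site reaction at Week 6. Under the 7.1.2 window this person has no event. Under the 7.6.2 aggregate the same person has one.

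At stake is whether the report will contain a proportion for the period that section 1.2.4 singles out. It cannot be derived from the other any-event proportions: those for Weeks 0–5, for first injection to 12 weeks after the last, and for the whole study do not determine the one for Weeks 29–81. The hormonal-contraception endpoint in 7.1.2 refers back to the safety endpoints defined above it, so it carries the same uncertainty.

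**Working it through.** The protocol states no event rate or precision for this endpoint, so there is no figure to reproduce. The check is a comparison of windows, followed by an illustration.

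**1. Windows by number of injections.** Tail window = last injection to last injection + 52. Aggregate window = Week 0 to the end of follow-up.

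| Injections received | Last injection | Tail window (7.1.2) | Aggregate window (7.6.2) | Extra weeks | Tail share |
|---|---|---|---|---|---|
| 3 | Week 29 | 29 to 29 + 52 = 81 | 0–81 | 29 | 52/81 = 64% |
| 2 | Week 17 | 17 to 17 + 52 = 69 | 0–69 | 17 | 52/69 = 75% |
| 1 | Week 5 | 5 to 5 + 52 = 57 | 0–57 | 5 | 52/57 = 91% |

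The end weeks agree with sections 5.12 and 5.15.

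**2. Is the tail window listed anywhere else?** The primary analysis in 7.6.2 stops 12 weeks after the last injection. The adverse-event tables in 7.6.2 are split into long-acting dosing, oral dosing and both combined. Section 7.6.3 adds no window for the 52 weeks after the last injection. None of these is the tail window.

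**3. Direction.** Each tail window lies inside the aggregate window. Anyone with an event in the tail therefore has one in the aggregate, and for the same participants the aggregate proportion is equal or larger. It is equal only if nobody's events are confined to the weeks before the last injection.

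**4. Illustrative size, three injections.** The rates are assumed. Let p be the proportion with an event over Weeks 29–81.

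- Constant hazard: P(0–81) = 1 − (1 − p)^(81/52).
- Hazard doubled in Weeks 0–29: P(0–81) = 1 − (1 − p)^((52 + 2 × 29)/52) = 1 − (1 − p)^(110/52).

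| Assumed p, Weeks 29–81 | Weeks 0–81, constant hazard | Weeks 0–81, early hazard doubled |
|---|---|---|
| 5% | 7.7% | 10.3% |
| 10% | 15.1% | 20.0% |
| 15% | 22.4% | 29.1% |
| 25% | 36.1% | 45.6% |
| 50% | 66.0% | 76.9% |

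**5. Ascertainment.** Detection is also uneven over time. Appendix I schedules blood count and chemistry at 14 enrollment and follow-up visits (Weeks 0, 2, 4, 5, 6, 9, 13, 17, 18, 23, 29, 30, 35 and 41). Only Weeks 30, 35 and 41 come after the third injection. At Weeks 53, 65, 77 and 81 the safety bloods are liver tests alone. Laboratory events in the aggregate can therefore be expected to come largely from the earlier weeks, which a constant hazard does not reflect.

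**The case against.** The strongest reply is that 7.6.2 may already do what was intended. The objective in 2.2 names the oral drug, which is taken only in the first four weeks. That favours a cumulative reading through 52 weeks after the last injection, which is the 7.6.2 aggregate. The closing phrase of the 7.1.2 bullet, on the aggregate phases, could also be meant to cover the safety half. This stands as a reason not to say that 7.6.2 is the section in error. It does not remove the mismatch. If the cumulative reading is right, 7.1.2 is misworded. If the closing phrase governs both halves, the bullet holds two incompatible windows, and neither is the one in 7.6.2, which includes follow-up.

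A reader might infer more than the text supports:

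- **That the tail proportion will never be computed.** Section 7.6.2 also says every safety endpoint will be tabulated by arm with exact intervals, and its list of secondary analyses is not worded as exhaustive. The supportable statement is that no such analysis is explicitly listed.
- **That the aggregate would be reported under the follow-up endpoint's name.** Nothing says so; 7.6.2 labels its window as the aggregate.
- **That early events conceal all later ones.** Participants count once per category at highest severity, so a later Grade 3 event supersedes an earlier Grade 2. Events are also tabulated by preferred term, and the expedited-event listing shows time since the last injection. What remains is narrower: the single any-Grade-2-or-higher proportion is not specific to the tail.

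Detail of a descriptive table can be left to a statistical analysis plan, which is not at hand here. But such a plan would have to follow one section and depart from the other. If the choice were made after the unblinding planned once the last active-arm participant completes Week 41 (sections 5.16 and 7.5), it could be made with knowledge of results.

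**Conclusion.** The protocol gives two different windows for one secondary safety proportion, and the objective does not decide between them. For a three-injection completer they are Weeks 29–81 and Weeks 0–81. No listed analysis is specific to the 52 weeks after the last injection.

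The direction of the difference rests on no assumed rate: in the same participants the aggregate is never smaller. The size is unknown. The illustration gives a gap of 5.1 points (15.1% − 10%) under constant hazard and 10.0 points (20.0% − 10%) with the early hazard doubled, when the tail rate is taken as 10%. These are assumed rates, not protocol figures, and they should not be read as a forecast or as showing that the protocol has a number wrong.

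The endpoint is secondary and descriptive, and section 7.6.2 disclaims formal treatment comparisons. The primary endpoint, sample size and data collection are untouched. This is a real inconsistency, worth correcting before unblinding, and limited in reach.

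**What to change.** Reconcile sections 2.2, 7.1.2 and 7.6.2 by stating two separately labelled endpoints, in the same words in each section:

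- (a) the proportion with a Grade 2 or higher clinical or laboratory event from the last injection received to 52 weeks after it, anchored to each participant's own last injection;
- (b) the cumulative proportion with such an event from Week 0 to the end of follow-up.

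Move the tolerability half of the 7.1.2 bullet into its own sentence with its own window. For the hormonal-contraception endpoint, say which of the safety endpoints it refers to.

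The cost is a few sentences and one extra descriptive table from data already collected. No visit, sample or participant is added.

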# 7.1.3 Exploratory Endpoints

• Relationships between observed AEs and pharmacokinetic parameters (including but not limited to GSK1265744 Cmax and Cmin and AUC) and participant demographic data (individual and in aggregate)

• Relationships between pharmacogenetics (evaluated by Genome Wide Association Study [GWAS], which will inform subsequent targeted analyses) and pharmacokinetic parameters or incidence of AEs (any and by organ class and individual AE)

# 7.2 Sample Size

We expect at least 160 (120 in 744LA and 40 in placebo) out of 176 participants who will complete the primary endpoint visit (week 41) assuming the annual retention rate to be approximately 90%. The following power calculations are based on the sample size of 160 (120 in 744LA and 40 in placebo).

The goal of the safety evaluation for this study is to identify safety concerns associated with 744LA. The ability of the study to detect SAEs (See Section 6.3) can be expressed by the true event rate above which at least 1 SAE would likely be observed and the true event rate below which no events would likely be observed. Specifically, for the 744LA arm of the study (n =120), there is a 90% chance of observing at least 1 event if the true rate of such an event is 2% or more, and there is a 90% chance of observing no events if the true rate is <0.1%. For the placebo arm (n=40), there is a 90% chance of observing at least 1 event if the true rate of such an event is 5.6% or more, and there is a 90% chance of observing no events if the true rate is 0.2% or less.

Probabilities of observing 0, 1 or more, and 2 or more events among the arms (N=160; 120 in 744LA arm, and 40 in placebo arm) are presented in Table 3 for a range of true adverse event rates. These calculations provide a more complete picture of the sensitivity of this study design to identify potential safety concerns with 744LA.

Table 3: Probability of observing 0 events, 1 or more events, and 2 or more events, among both arms: the 744LA arm (n=120) and the placebo arm (n=40), for different true event rates.

True event						
rate (%)	Pr(0/120)	Pr(1+/120)	Pr(2+/120)	Pr(0/40)	Pr(1+/40)	Pr(2+/40)
0.5	54.8	45.2	12.2	81.8	18.2	1.7
1	29.9	70.1	33.8	66.9	33.1	6.1
2.5	4.8	95.2	80.5	36.3	63.7	26.4
5	0.2	99.8	98.4	12.9	87.1	60.1
10	< 0.1	>99.9	>99.9	1.5	98.5	92
15	< 0.1	>99.9	>99.9	0.2	99.8	98.8

The primary safety endpoint is the proportion of participants experiencing any Grade 2 or higher clinical AEs and laboratory abnormalities that occur from the initial injection to 41 weeks among participants who receive at least one injection. The precision with which the true event rate can be estimated from the observed data depends on the underlying true event rate and the sample size. Table 4 shows the two-sided 95% confidence intervals for the true event rate based on various values for the observed event rates, given the sample size of 120 in 744LA arm and 40 in placebo arm. Calculations are done using the score test method.

Table 4. Two-sided 95% confidence intervals based on observing a particular rate of event for the 744LA arm (n=120) and the placebo arm (n=40)

Observed Event	95% CI (744LA arm)	95% CI (Placebo arm)
Rate (%)		
0	(0, 3.1)	(0, 8.8)
2.5	(0.9, 7.1)	(0.4, 12.9)
5	(2.3, 10.5)	(1.4, 16.5)
10	(5.8, 16.7)	(4, 23.1)
15	(9.7, 22.5)	(7.1, 29.1)
20	(13.8, 28)	(10.5, 34.8)
25	(18.1, 33.4)	(14.2, 40.2)

The safety and toxicity rates of people using 744LA and the rates for those using placebo will not be formally compared. A sample size of 160 participants (120 in 744LA and 40 in placebo) assuming 90% retention rate per year will assure with 82% power that a 95% confidence interval for the difference between the study drug and placebo safety and toxicity rates has an upper limit no more than 10% when the true toxicity rates for 744LA and placebo are both 5%. Table 5 displays two-sided 95% confidence interval for different assumptions on the safety and toxicity rates in the active product and placebo arms for a study of this sample size.

Table 5: Two-sided 95% Confidence Intervals for the Difference between 744LA and Placebo Safety Rates (n=120 in the 744LA arm and n=40 in the placebo arm)

Assumed rate	Assumed rate in 744LA arm											
in placebo arm	1% 5%		7.5%	10.0%	12.5%	15.0%						
1%	(-3.6, 3.6)	(-1, 9)	(0.9, 12.1)	(2.8, 15.2)	(4.8, 18.2)	(6.9, 21.1)						
5%	-	(-7.8, 7.8)	(-5.7, 10.7)	(-3.6, 13.6)	(-1.5, 16.5)	(0.7, 19.3)						
7.5%	-	1	(-9.4, 9.4)	(-7.3, 12.3)	(-5.1, 15.1)	(-2.9, 17.9)						
10.0%				(-10.7,	(05.105)	( ( 2 1 ( 2 )						
	-	-	-	10.7)	(-8.5, 13.5)	(-6.3, 16.3)						
12.5%					(-11.8,							
12.5 /0	-	-	-	-	11.8)	(-9.6, 14.6)						
15.0%						(-12.8,						
15.0 / 0	-	-	-	-	-	12.8)						

The tolerability of 744LA will be measured by the proportion (with 95% CI) of participants who terminate from receiving injections prior to the full course due to AE, intolerability of injection, frequency of injections, or burden of procedures related to injections out of those subjects that received at least one injection by treatment arm. Table 4 shows two-sided 95% confidence intervals for true tolerability rate based on various possible observed rates, given the sample size of 120 participants in the 744LA arm.

The acceptability of 744LA will be measured by the proportion (with 95% CI for the 744 LA arm) of participants who would consider using 744LA for HIV prevention in the future. This endpoint will be measured at the end of the study on every enrolled participant (including those who terminated product use during the trial). Table 6 shows two-sided 95% confidence intervals for true acceptance rate based on various possible observed rates, given the sample size of 120 participants in the active 744LA arm

Table 6: 95% Confidence Intervals for the True Acceptance Rate Given Possibly Observed Rates

N	Observed Event Rate	95% CI for True Event Rate
	50%	(41.2%, 58.8%)
	70%	(61.3%, 77.5%)
Arm 1: 120 (744LA)	80%	(72%, 86.2%)
	90%	(83.3%, 94.2%)
	95%	(89.5%, 97.7%)

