#### 1.4 Clinical Experience to Date – GSK1265744

As of June 30, 2013, 483 adult subjects have been exposed to at least one dose of GSK1265744 in sponsored Phase I-IIb clinical trials. GSK1265744 has been evaluated in ten Phase I/IIa clinical pharmacology studies (eight studies in healthy HIV-uninfected subjects; one study in healthy HIV-uninfected subjects and HIV-infected subjects; and one study in HIV-infected subjects only), as well as one Phase IIb clinical study utilizing oral 744. Four studies are currently ongoing (3 Phase I studies and 1 Phase IIb study).

Oral 744 has been studied at doses between 5 mg - 150 mg in HIV-uninfected and HIV-infected adults. The oral formulation of GSK 1265744 has been generally well-tolerated as single or repeated doses in clinical studies of HIV-uninfected adults. Among the HIV-uninfected and HIV-infected subjects who received oral formulations ranging from 5 mg-150 mg in Phase 1 and 2a studies, three subjects receiving oral 744 were withdrawn due to drug-related adverse events (AEs), including dizziness, leucopenia, and aspartate aminotransferase and alanine aminotransferase [AST/ALT]/gamma-glutamyltransferase increase. No drug-related Grade 3 or Grade 4 AEs or serious adverse events (SAEs) were reported 46.

In total, 136 HIV-uninfected subjects have received single or repeat doses of 744LA 100-800 mg IM or subcutaneous (SC) injections alone or in combination with long acting RPV (TMC278 LA). To date there have been no drug-related Grade 3 or Grade 4 AEs or SAEs and only one subject withdrew due to an AE (self-limited Grade 1 rash) following 744LA. Two non-drug related SAEs have been reported: foot osteomyelitis and elective hysterectomy. Injection site reactions (ISR) occurred in the majority of subjects following IM (76% with any ISR) dosing, however, the reactions were mild and moderate (overall ISR Grade 2: 14% in IM without any Grade 3 or 4 ISRs). ISRs related to 744LA injection were common but generally mild (IM: 86%, SC: 99%) with no Grade 3 ISR AEs. The most frequent ISRs for IM dosing were pain (71%), erythema (9%) and nodules (7%)C 2013). Median IM ISR durations were approximately 5 days for pain and erythema, and approximately 22 days for nodules.

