# 6.3 Adverse Event Definition and Reporting

An adverse event (AE) is defined as any untoward medical occurrence in a clinical research participant administered an investigational product and which does not necessarily have a causal relationship with the investigational product. As such, an AE can be an unfavorable or unintended sign (including an abnormal laboratory finding, for example), symptom or disease temporally associated with the use of an investigational product, whether or not considered related to the product.

Study participants will be provided a 24-hour telephone number and contact information and instructed to contact the study clinician to report any AEs they may experience. For lifethreatening events, they will also be instructed to seek immediate emergency care. Where feasible and medically appropriate, participants will be encouraged to seek evaluation where the study clinician is based, and to request that the clinician be contacted upon their arrival. With appropriate permission of the participant, whenever possible, records from all non-study medical providers related to AEs will be obtained and required data elements will be recorded on study

CRFs. All participants reporting an AE will be followed clinically, until the AE resolves (returns to baseline) or stabilizes.

Study site staff will document in source documents and the appropriate CRF all AEs (Grade 1 and higher) reported by or observed in enrolled study participants regardless of severity and presumed relationship to study product. AE severity will be graded per the DAIDS Table for Grading Adult and Pediatric Adverse Events, Version 1.0, December 2004 (Clarification dated August 2009), or most current version.

Relatedness is an assessment made by a study clinician of whether or not the event is related to the study agent. The relationship of all AE to study product will be assessed as specified in Version 2.0, January 2010 (or most current version) of the DAIDS Expedited Adverse Event (EAE) Reporting Manual.

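### The only assurance probability for the arm difference (82%) is stated at a 5% event rate, which does not fit a primary endpoint that counts Grade 2 injection-site reactions

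*Protocol*

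**What the plan says.** Section 7.2 bases its calculations on 160 participants, 120 on 744LA and 40 on placebo, after allowing for about 90% annual retention. It claims 82% power for the 95% interval around the arm difference to meet this condition: "upper limit no more than 10% when the true toxicity rates for 744LA and placebo are both 5" percent. No other assurance probability is given for the arm difference. Around it stand detection probabilities for each arm (Table 3), single-arm intervals for observed rates up to 25% (Table 4) and intervals for the difference at assumed rates up to 15% (Table 5). The same section says that the two arms' rates will not be formally compared.

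Section 7.1.1 defines the primary safety endpoint as "Proportion of participants experiencing any Grade 2 or higher clinical AEs and laboratory abnormalities that occur from the initial injection to Week 41". It covers only those who had one injection or more, and it makes no exception for ISRs. Section 6.3 defines an adverse event broadly, to include any "symptom or disease temporally associated with the use of an investigational product, whether or not considered related to the product", and ISRs meet that definition. Section 1.4 itself refers to them as AEs, and Section 7.6.2 tabulates them under the primary analyses.

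On earlier experience with IM 744LA, Section 1.4 reports any ISR in 76% and "overall ISR Grade 2: 14% in IM without any Grade 3 or 4 ISRs". It also describes 86% of IM reactions as mild.

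**The concern.** The assurance is computed for an event that occurs in 5% of each arm. The endpoint it describes is a composite of all Grade 2 or higher clinical and laboratory events over the injection phase. One component alone, Grade 2 ISRs, is reported in the protocol's own background section at a figure well above 5% for the active product. Nothing in the protocol supports 5% for the composite.

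Since no hypothesis test is planned, the sample size is justified by statements of precision and detection. A reader who takes the 82% as the expected precision of the primary arm difference would expect the upper limit to fall within 10 points. At the event rates that the protocol itself suggests, this is unlikely.

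**Working it through.** **Inputs.** n1 = 120 and n0 = 40; two-sided 95% interval; bound of 10 points; planning rates of 5% and 5% (all Section 7.2). ISR figures of 76% (any) and 14% (Grade 2) come from Section 1.4.

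**Method.** Let X ~ Bin(120, p1) and Y ~ Bin(40, p0) be independent. The unpooled Wald upper limit is

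U = X/120 − Y/40 + 1.96 × √[ (X/120)(1 − X/120)/120 + (Y/40)(1 − Y/40)/40 ].

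The assurance is the sum of P(X = x)·P(Y = y) over all pairs (x, y) with U ≤ 0.10.

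**Reproducing the plan.** At p1 = p0 = 5% this gives 82.4%, in agreement with the stated 82%. The half-width at the assumed rates is 1.96 × √[0.05 × 0.95 × (1/120 + 1/40)] = 7.8 points, in agreement with Table 5.

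**Active-arm rate implied by Section 1.4.** There are two readings of the 14%:
- It is a share of subjects: 14%.
- It is a share of reactions. This is suggested by 86% mild + 14% Grade 2 = 100%. If each affected subject has one grade (an assumption), the share of subjects is 0.76 × 0.14 = 10.6%.

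Both count ISRs only; no other Grade 2 event is added to the active arm. The protocol gives no ISR rate for placebo injections, so the placebo rate is taken either at the plan's 5% or as equal to the active rate. The 7.5% rows show what happens if Grade 2 reactions cluster in fewer subjects.

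**Results.** The upper limit is computed at the assumed rates, for example 14% versus 5%: 9.0 + 1.96 × √(0.14 × 0.86/120 + 0.05 × 0.95/40) × 100 = 9.0 + 9.2 = 18.2 points. The last column is the range over exact Wald, exact Newcombe, exact score and the normal approximation.

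| 744LA | Placebo | Upper limit (points) | Assurance, exact Wald | Range over four methods |
|---|---|---|---|---|
| 5% | 5% | 7.8 | 82% | 71–83% |
| 7.5% | 5% | 10.7 | 46% | 43–54% |
| 10.6% | 5% | 14.3 | 14% | 14–22% |
| 14% | 5% | 18.2 | 3% | 3–6% |
| 7.5% | 7.5% | 9.4 | 60% | 55–71% |
| 10.6% | 10.6% | 11.0 | 43% | 43–58% |
| 14% | 14% | 12.4 | 34% | 34–47% |
| 20% | 20% | 14.3 | 26% | 26–36% |

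For equal rates p the half-width reduces to 1.96 × √[p(1 − p)/30], since 1/120 + 1/40 = 1/30. At 20% this is 1.96 × √(0.16/30) = 14.3 points. With no true difference, the interval is therefore already wider than the 10-point bound at 10.6%.

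**The case against.** The strongest reply is that the sentence is conditional and true. It names its 5% rates, and the 82% follows from them. Table 5, directly below it, gives upper limits of 19.3 points at 15% versus 5% and 12.8 points at 15% in both arms, so an attentive reader can see the 10-point bound fail near the 14% figure. Table 6 gives n = 120 intervals for a proportion of 50% and above. No decision depends on the assurance, because no formal comparison is planned and Section 7.6.2 makes any p-values descriptive. All of this stands, and it limits the consequence. It does not make 5% a suitable rate at which to state the only assurance probability.

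The input is also soft. Besides its unclear denominator, the 14% comes from doses of 100–800 mg, given once or repeatedly. The 10.6% is not a floor, since clustering would lower it. At 7.5% versus 5%, however, the assurance is still only 46%. The inclusion of ISRs follows from the adverse event definition and the absence of an exclusion; it is not stated outright.

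A reader might infer more than the documents support:
- That the true assurance is below 1%. This follows if an independent 5% background is added to a 14% ISR rate (1 − 0.95 × 0.86 = 18.3%) and placebo stays at 5%. It requires independence and no Grade 2 ISRs on placebo, although placebo participants also receive two IM injections at each of three visits.
- That the 14% should be compounded over three injection visits. Section 1.4 does not give it as a per-visit rate.
- That many repeated laboratory tests make a 5% composite rate unattainable. This needs independence between repeated tests in one person, and grading thresholds that the protocol cites but does not reproduce.
- That the primary analysis could not reveal a systemic safety problem. Section 7.6.2 tabulates ISRs by type, severity and injection, and adverse events by preferred term, severity and relationship, so other events remain visible.

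**Conclusion.** The concern holds as a mismatch between the planning rate and the endpoint. The 82% is arithmetically correct at 5% in both arms, but that rate conflicts with the protocol's own ISR data for the endpoint as defined. On the two readings of the 14%, the assurance is about 3% or 14% with placebo at 5%, and 34% or 43% with equal arms. None of the four methods brings these cases above 58%.

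The conclusion rests on ISRs counting as adverse events in the primary endpoint and, for the 10.6% reading, on one ISR grade per affected subject. It does not show an error of calculation, an inadequate sample size or an uninterpretable primary result. The stated precision should be corrected.

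**What to change.** 1. In Section 7.2, replace the 82% sentence with the assurance at rates plausible for the endpoint including ISRs, for both equal and unequal arms. Alternatively, say that 82% applies only to a named type of event for which 5% is credible.
2. Extend Table 5 above 15% and the placebo column of Table 4 above 25%.
3. State how the 14% in Section 1.4 is defined (subjects or reactions), so that the chosen planning rate can be traced.
4. Report the proportion of participants with a Grade 2 or higher event, and the arm difference, also excluding ISRs. This is a supportive line; the primary endpoint stays as it is.

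The cost is a revised paragraph, some added table rows, one extra line in the results table and stated precision that looks less favourable. Sample size, visits and conduct are unaffected.
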